This will be a pilot randomised, non-blinded, single center trial in children with CF attending the RCH on highly effective modulators. The study will compare usual care to an intervention arm, with the intervention being the new remote symptom monitoring and automated treatment plan model of care.

Participants:

Participants will be children with a confirmed diagnosis of Cystic Fibrosis under the care of RCH, on a highly effective modulator (ETI or ivacaftor) and their caregiver. Participants will be included in the study only if they meet all of the inclusion criteria and none of the exclusion criteria.

Inclusion criteria:

- Diagnosis of Cystic Fibrosis
- On ETI or ivacaftor for a minimum of 2 weeks
- Clinically stable without antibiotic treatment for a pulmonary exacerbation in 2 weeks prior to consent
- Attending RCH CF clinic
- Able to complete home spirometry (standard of care for all children with CF >5 years at RCH CF clinic)
- Sufficient English to complete a survey
- Access to a smart phone to access remote symptom monitoring surveys

Exclusion criteria:

- Participants not signed up or not willing to sign up to the RCH Portal (note that 80% of RCH CF patients are already signed up to the portal)
- Participants who do not have access to a smartphone or computer on a daily basis
- Participants who do not have access to a home spirometer for lung function purposes
- Participants will be excluded from the study for technological access reasons such as lack of access to the RCH Portal and IT equipment as this is the basis of the intervention.

Sample:

Although this is a randomised controlled trial it is a pilot and currently there is no known sample size in the literature relating to a pilot trial. However, we will aim to include a minimum of 30 participants in the study in line with other pilot trials conducted by CI [name] [27]. We believe this will give us sufficient data on the feasibility and acceptability of the new model of care and potential effectiveness. If the intervention is feasible and acceptable the outcome data, which can be collected with minimal burden on participants and resources, will be crucial to inform sample size calculations for fully powered RCTs.

Study Name: Acceptability, feasibility and impacts of remote symptom monitoring and automated treatment plans in children with Cystic Fibrosis (CF) on highly effective modulators: a pilot randomised controlled trial.

Protocol Number: 91117

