Version & date: version 2, 28.10.2022

Recruitment:

Potential participants will be recruited through the following multi-pronged approach:

Patients

- *Self-enrolment:*

Participants will be sent information regarding the study, including study overview and contact details for the study team, in a letter signed by the CF centre director via the RCH Portal (Appendix 1). The letter will include a QR code taking interested families directly to a screening questionnaire for study eligibility (Appendix 2). If meeting eligibility criteria the participant will be linked to the PICF (Appendix 3) where they can read in more detail about the study. There will also be a child information sheet regarding the study. Families will indicate consent by checking a box at the start of the online survey and will subsequently be recruited into the study. Families will then complete the baseline demographic survey (Appendix 4). The initial demographic survey will include an item seeking their permission to contact them to potentially participate in a qualitative interview via MS Teams if allocated to the intervention arm. These families will be invited to include a preferred contact mode (either email or telephone) and a member of the research team will contact parents or carers via their preferred contact mode to invite them to participate in the interview.

- *Phone call enrolment:*

For those who do not self-enrol from the initial letter, a follow up phone call will be made by the principal investigator (an RCH CF physiotherapist) one week after letter has been sent out, to ascertain interest in the study. The principal investigator will explain the study to the potential participant. Interested families will complete the screening survey (Appendix 2) over the phone with the PI and will be sent links to the: 1) PICF (Appendix 3), 2) Online consent, and 3) Baseline demographic survey (Appendix 4) by the RCH portal.

- *Clinic enrolment (face to face or via telehealth):*

Potential participants attending their routine CF clinic may be approached by the principal investigator to ascertain their interest in the study. The principal investigator will explain the study to the potential participant. Interested families will complete the: 1) screening survey (Appendix 2) 2) PICF (Appendix 3), 3) consent, and 4) Baseline demographic survey (Appendix 4) in person or if time does not permit will be sent links by the RCH portal.

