CF MDT will be sent a PICF (Appendix 6) describing the purpose of the trial and inviting them to participate in semi-structured interviews. Once consent has been gained, the PI will contact them to make a time for the semi-structured interview.

Randomisation:

Randomisation will occur after consent in signed and will be performed by a person independent to the study. A stratified randomization will be employed with the goal of ensuring balance between study arms by risk category employed by the RCH CF team. The randomisation schedule will be created by computer-generated random numbers, before the first participant has been recruited. The participant cohort will be stratified by child risk category (2 levels of category: 1 Very high risk & high risk and 2 Medium risk & low risk). Within each strata, permuted block randomisation will be used to ensure balance between the intervention and control group. A randomly generated sequence of block sizes containing 2, 4, or 6 participants will be used. This will help ensure balance in numbers between intervention and control groups, prevent potential confounders of risk category type impacting the measurement of outcomes, and prevent any predictability in intervention allocation[28]. The schedule will be held by an independent person, and allocation will not be

revealed prematurely to CI. Because of these procedures, the research team will be unable to predict which group the participant will be allocated to.

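### The claim that allocation cannot be predicted does not hold for small open-label blocks: a recruiter who knows past allocations could guess about 69% correctly (chance 50%), with the opening mainly in clinic enrolment

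*Protocol*

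**What the plan says.** All references are to the protocol.

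- **Design.** "This will be a pilot randomised, non-blinded, single center trial in children with CF" (Trial Design, Design). The Sample paragraph sets the size: "we will aim to include a minimum of 30 participants in the study".
- **Strata.** The child's risk category as used by the hospital's own CF team, in "2 levels of category: 1 Very high risk & high risk and 2 Medium risk & low risk" (Randomisation).
- **Method.** Within strata, "permuted block randomisation will be used to ensure balance between the intervention and control group". On block size: "A randomly generated sequence of block sizes containing 2, 4, or 6 participants will be used".
- **Safeguards.** The schedule is generated before the first child is recruited. A person independent of the study holds it and allocates after consent, and early disclosure to the chief investigator is barred.
- **Claims drawn from this.** One sentence says that the varying blocks rule out predictability altogether. A second says that "the research team will be unable to predict which group the participant will be allocated to".
- **Recruitment.** There are three routes: self-enrolment from a portal letter; a phone call by the principal investigator, one week after the letter, to families who have not enrolled; and clinic, where "Potential participants attending their routine CF clinic may be approached by the principal investigator to ascertain their interest in the study".

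**The concern.** An independent list holder hides the list, but not the allocations already made, which in an open single-site trial can become known to the clinical team. Balanced blocks as small as 2 pull each stratum back to equality quickly, so the arm that is behind is the likelier next allocation. The strata are the team's own risk classes, so staff could track them.

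A recruiter with a better-than-chance guess and some freedom over whom to approach could, knowingly or not, match families to the expected arm by likely engagement or severity. A two-level risk stratum would not remove that. There is room for choice: the Recruitment section counts 100 portal-registered children on the eligible drugs for a minimum of 30 places, and recruitment may stop once the minimum is reached.

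The exposed results are those compared between arms in section 6: team-family contacts (a primary measure), exacerbations, FEV1 change, admissions, quality of life and costs. The Sample paragraph intends the outcome data to inform the size of a full trial.

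**Working it through.** The protocol gives no figure for predictability, so there is none to reproduce.

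**Inputs from the protocol:** blocks of 2, 4 or 6; two strata; minimum 30 children; open, one site.

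**Assumptions, because the protocol is silent:** block sizes equally likely; 1:1 allocation (implied by even blocks and the balance aim); 15 children per stratum, with other splits tried; the recruiter knows all earlier allocations in the stratum.

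**1. Early allocations by hand.**
- Second child in a stratum goes to the opposite arm from the first: (1 + 2/3 + 3/5)/3 = 76%.
- If the first two match, the block is 4 or 6. Two alike has probability 1/3 in a block of 4 and 2/5 in a block of 6, so block 4 has posterior (1/3)/(1/3 + 2/5) = 0.455. The third child goes opposite with probability 0.455 × 1 + 0.545 × 0.75 = 86%.

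**2. Guess the arm that is behind, and toss a coin when tied.** In a complete block of 2m, the expected number of correct guesses is m + (4^m/C(2m,m) − 1)/2.
- Block 2: 1 + (4/2 − 1)/2 = 1.50 of 2, or 75.0%.
- Block 4: 2 + (16/6 − 1)/2 = 2.83 of 4, or 70.8%.
- Block 6: 3 + (64/20 − 1)/2 = 4.10 of 6, or 68.3%.
- Equal mix, long run: (1.50 + 2.83 + 4.10)/(2 + 4 + 6) = 8.43/12 = 70.3%.

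**3. Thirty children, last block cut off at the stratum size (exact enumeration).**
- Strata 15/15: 68.6%. Splits of 12/18, 10/20, 8/22 and 5/25: 68.6% to 69.5%.
- Random stratum membership (simulation): mean 69.0%, middle 95% of trials 63% to 73%.
- In a 15/15 trial, 0.686 × 30 = 20.6 correct guesses against 15 by chance.

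**4. Sensitivity.**
- Unequal use of block sizes, stratum of 15: 66% (all 6) to 73% (all 2).
- Recruiter does not track strata: about 64%.
- Best possible guesser who knows the block sizes: about 69-70%, almost no gain over the simple rule. Only 3-4% of allocations are certain.

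**5. Alternatives, stratum of 15.** Fifteen is odd, so an imbalance of 1 is the floor.

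| Schedule | Guessed correctly | Mean final imbalance (children) |
|---|---|---|
| Blocks 2, 4, 6 (as written) | 69% | 1.0 |
| Blocks 4, 6, 8 | 66% | 1.1 |
| Big stick, limit 3 | 56% | 1.7 |

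**6. Where a guess could be used.**
- *Self-enrolment:* the family acts on a letter; the investigator makes no selection.
- *Phone:* the protocol fixes who is called (those who have not enrolled) and when (one week after the letter).
- *Clinic:* families may be approached, with no rule on which or in what order. This is the discretionary route.

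**The case against.** Randomly varied permuted blocks with an independent list holder and allocation after consent are a legitimate, common compromise between balance and predictability. The protocol nowhere says that the principal investigator receives a running tally of allocations; that is inferred from the open design. Even in clinic, a family short of time completes consent later through portal links, and other families self-enrol in between, so guessing the next slot does not place a chosen child in it. Survey completion, task completion and the interviews concern the intervention model, so most primary measures are not between-arm contrasts.

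All of this stands, and it limits the point. It does not rescue the two absolute statements: concealing the list is not the same as preventing prediction, and nothing in the protocol keeps past allocations from the recruiter.

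Stronger readings are tempting but unsupported:

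- *About 69% of allocations are known in advance.* The gain over chance is about 19 points, and very few allocations are certain.
- *A bias of about 0.19 SD.* This comes from 2 × 0.25 × (2 × 0.686 − 1), where the 0.25 SD shift is assumed and applied to every enrolled child in the direction of the guess. The protocol supports neither step.
- *The fault is that the block sizes are printed.* Hiding them gains almost nothing, because the simple rule does not use them.

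**Conclusion.** The claim of unpredictability is wrong for this design and should be corrected. A recruiter aware of earlier allocations could call about 69% correctly (66-73% across block-size mixes; about 64% without tracking strata) against 50% by chance. This rests on equally likely block sizes for the central figure, 1:1 allocation, and knowledge of past allocations that the open design permits but the protocol does not state.

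The protocol shows an opportunity for selective enrolment, mainly in clinic, and not that it would occur. Any bias scales with the unknown share of children enrolled there and is confined to the between-arm comparisons; no magnitude can be derived. The point justifies inexpensive corrections and does not require replacing permuted blocks.

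**What to change.** 1. **Recruitment, clinic enrolment.** State that every eligible clinic attendee is approached consecutively, or in an order fixed in advance by the independent person. This is the most useful change, because it leaves a guess little to act on.
2. **Randomisation, block sizes.** Drop size 2, for example by using 4, 6 and 8. Correct guesses fall from about 69% to 66%, and mean imbalance in a stratum of 15 moves from about 1.0 to 1.1 children.
3. **Randomisation, wording.** Replace the two absolute statements with one saying that the list is concealed from the research team but that some prediction from past allocations remains possible in an open trial.

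A big-stick schedule is an option if the sponsor values unpredictability more than balance: about 56% guessed, at about 1.7 children of imbalance per stratum. With a minimum of 30 children and balance as a stated aim, that is a trade-off for the sponsor to decide and not a required change.

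The cost is a short amendment and a new computer-generated list from the same independent person, with no extra children or staff. It should be done before the schedule is generated, which the protocol places ahead of the first recruitment.

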4 STUDY VISITS AND PROCEDURES

Study timeline:

Information relating to study sent via letter		
Opportunity for self-enrolment, clinic enrolment, phone enrolment		A
Consent		B
Randomisation	Intervention	Control
Baseline data collection	C D E	C D E
3 months	F G H	F G
6 months	F G	F G
12 months	D E F G H	D E F G
A	Survey screening for inclusion/exclusion criteria sent to all potential participants	
B	Children meeting inclusion criteria and interested in study referred to PICF and consent form	
C	Demographic information (as part of the baseline questionnaire)	
D	Spirometry	
E	CFQ-R & EQ-5D-Y (as part of the baseline questionnaire)	
F	Data download from EPIC (admissions, LOS, contacts with CF team)	
G	Online follow up questionnaire	
H	Semi structured interviews	

Description of intervention

Remote symptom monitoring and automated treatment plans:

Participants randomised to the intervention arm will receive onboarding material (Appendix 7) detailing instructions of how to access and use the remote monitoring system via the RCH portal.

Participants will be asked to complete two surveys:

1. Baseline symptom survey (Appendix 8)

Participants will be prompted to complete survey by a push notification sent to their mobile phone and built into EPIC at the:

- Commencement of the trial;
- Each month post commencement of the trial; and
- After each exacerbation is detected.

2. Twice weekly symptom survey (Appendix 8)

Participants will be prompted to complete a survey by a push notification sent to their mobile phone and built into EPIC twice a week

The survey is a validated tool for detecting pulmonary exacerbations in people with CF[29].

A score is assigned to each survey field. Every symptom-monitoring questionnaire completed by the patient or patient's family is compared to their last known baseline questionnaire.

If the frequency or severity of **two or more symptoms** have worsened compared to baseline, the **Exacerbation Pathway** is triggered (Appendix 9 for exacerbation calculations).

If the system detects an exacerbation, it will send an automated treatment plan out to the patient and their caregiver including:

- Directions to commence a specific antibiotic
- Directions to change/or increase airway clearance and inhalation therapy.

Information regarding antibiotic, airway clearance and inhalation therapy prescription will be extracted from the participant's EPIC file.

At this time participants will be asked to complete their **symptom survey on a daily basis**.

A message will be sent to the CF team alerting them of the exacerbation and the results of the symptoms survey. The RCH respiratory lab will book a telehealth appointment to perform home lung function to provide further detail of the exacerbation. Lung function will be performed at the start of the exacerbation and at 10-14 days later.

10-14 days after the exacerbation pathway is triggered, the program will assess if symptoms reported in the daily symptom survey have returned to baseline or not.

If the patient symptoms return to (or are better than baseline) on day 10-14:

Study Name: Acceptability, feasibility and impacts of remote symptom monitoring and automated treatment plans in children with Cystic Fibrosis (CF) on highly effective modulators: a pilot randomised controlled trial.

Protocol Number: 91117

Version & date: version 2, 28.10.2022

1. The program re-assigns the non-exacerbation tasks:
 - a. Monthly baseline questionnaire
 - b. Symptom-monitoring questionnaire (twice a week).
2. An automated In Basket message will be sent to the CF team notifying them that the exacerbation has ceased.
3. An automated message is sent to notify the participant that symptoms have improved and the exacerbation has ceased, instructing them to cease antibiotics (if not already), return to baseline airway clearance and inhalation therapy and complete their normal twice weekly symptom surveys.

If the patient symptoms do not improve on day 10-14 (Extended Exacerbation):

1. An In Basket Message will be sent to the CF team prompting for a clinical review via telehealth.
2. A notification will be sent to the participant via the portal notifying them that their symptoms have not become better and expect contact from the treatment in 24 hours.

The RCH EMR team have designed a workflow for the pilot to help assist in ensuring all aspects of care are completed.

Participants randomised to the intervention group will also receive all aspects of usual care in

addition to the above information, including quarterly visits to the CF clinic.

Usual Care:

Participants in the control arm will receive usual which consists of quarterly CF clinic visits and more urgent visits triggered by telephone calls from families concerned about their child's clinical status. This model of care relies on the participant/caregiver contacting the CF team if they notice a change in their symptoms.

Questionnaires

All online questionnaire links will be sent to participants via the portal.

Screening questionnaire:

A once off screening questionnaire will be linked to the initial study letter for participants to fill out prior to accessing the PICF and consent forms (Appendix 2).

Baseline:

Demographic questionnaire and data collection

A baseline demographic survey will be sent to all participants after online consent is gained (Appendix 4). Patient demographic and baseline data will also be collected via the EMR (Appendix 11)

Cystic Fibrosis Questionnaire- R (CFQ-R)

The CFQ-R (Appendix 12) is a validated questionnaire used to assess the health-related quality of life of people with CF of all ages [30]. It contains five generic domains, four specific domains, three

symptom scales and an overall health perception scale. It takes approximately 10 minutes to complete and can be self-administered.

EQ-5D-Y

The EQ-5D-Y (Appendix 13) is a validated survey assessing quality of life in a range of populations including CF [31]. It is a five-dimension survey encompassing mobility, looking after myself, doing usual activities, having pain or discomfort and feeling worried, sad or unhappy. It takes approximately 3 minutes to complete

3, 6 & 12 month follow up survey

A follow up survey will be sent to both the intervention and control group at 3, 6 and 12 months and will ask about number of pulmonary exacerbations, and data for health economics evaluation (e.g. time off work, travel costs) and information relating to burden of trial (Appendix 10)

At 12 months the *CFQ-R* and *EQ-5D-Y* will be completed also.

Procedures:

Spirometry

Spirometry will be performed either in person or via telehealth as is usual care for children with CF. Spirometry and lung volumes will be measured in accordance with international standards, utilising Jaeger Masterscreen body or Pneumo respiratory function equipment [32]. All pulmonary function testing will be carried out by experienced paediatric physiologists. If spirometry is performed at RCH, height will be measured to the nearest 0.1cm utilising a stadiometer (Seca) and weight will be measured with minimal clothing the nearest 0.1kg (Tanita). In keeping with current clinical practice, for spirometry performed via telehealth, anthropometric data will either be reported from measurements taken at home or the most recent in hospital measurements will be used.

Interviews:

Semi structured interviews (caregivers)

The initial demographic survey will include an item seeking caregiver permission to contact them to participate in a qualitative interview via MS Teams if in the intervention arm. These families will be invited to include a preferred contact mode and a member of the research team will contact caregivers via their preferred contact mode to invite them to participate in the interview. The PICF (Appendix 3 & 5) will outline that any interviews as a part of the study are purely voluntary.

Semi-structured interviews will be scheduled based on feasibility and preference. At the initial time of consent, the researcher will describe to the participants the reason for conducting the interview by providing a copy of the PICF (Appendix 3 & 5). The researcher will invite and respond to any questions or concerns from participants and invite participants to sign a consent form.

Participants will be informed of confidentiality procedures and that the interview will be audio recorded on MS Teams for research purposes. The participant will be advised that they can turn off their camera if they do not wish for a visual image to be recorded. If participants decline to be recorded, the interview will proceed with the PI taking notes of discussion. Prior to commencing the interview, the researcher will inform participants that they are able to stop the interview at any time

and revoke their consent to participate during or after the interview. In this event, interview recordings and transcripts will be removed from the study and destroyed. The withdrawal of participants at any part of the study will not affect their care in any way.

We aim to conduct interviews with up to 15 parents. The interviews aim to understand caregiver's experiences of the new model of care, including potential benefits, risks, ease of use and future improvements. Interview guide for parent semi structured interviews can be found in Appendix 14.

Semi structured interviews (CF MDT)

Members of the CF MDT will be approached by the principal investigator via email to ascertain their interest in participating in a semi-structured interview. Interviews will be scheduled based on feasibility and preference.

At the initial time of consent, the researcher will describe to the participants the reason for conducting the interview by providing a copy of the PICF (Appendix 6). The researcher will invite and respond to any questions or concerns from participants and invite participants to sign a consent form.

Participants will be informed of confidentiality procedures and that the interview will be audio recorded on MS Teams for research purposes. The participant will be advised that they can turn off their camera if they do not wish for a visual image to be recorded. If participants decline to be recorded, the interview will not proceed. Prior to commencing the interview, the researcher will inform participants that they are able to stop the interview at any time and revoke their consent to participate during or after the interview. In this event interview recordings and transcripts will be removed from the study and destroyed.

We will aim to perform interviews with as many members of the CF MDT as possible, aiming a minimum of 5 staff members. The interview guide for CF MDT semi-structured interviews can be found in Appendix 15 and aims to explore experiences of the new model of care, including potential benefits, risks, ease of use and future improvements.

EPIC reports

Pre-made reports have been created in EPIC associated with the remote symptom monitoring and automated treatment plan model of care. The report collates the following information for intervention group participants only:

- Number of baseline surveys completed
- Number of symptom surveys completed
- Number of exacerbations
- Length of exacerbation
- Symptoms experienced with exacerbation
- Number of airway clearance tasks completed.

This will assist with monitoring of intervention uptake and feasibility.

Other data to be collected from EPIC across the intervention and control groups include:

- Number of hospital admissions due to pulmonary exacerbation
- Hospital length of stay
- Number of CF specific outpatient appointments (face to face and telehealth)

Study Name: Acceptability, feasibility and impacts of remote symptom monitoring and automated treatment plans in children with Cystic Fibrosis (CF) on highly effective modulators: a pilot randomised controlled trial.

Protocol Number: 91117

Version & date: version 2, 28.10.2022

- Number of contacts made with participants (portal messages, phone, email)

These data will inform the health economic analysis.

Discontinuation of intervention

Participants are free to withdraw from the trial at any time upon their request or the request of their legally acceptable representative. Withdrawing from the trial will not affect their access to standard treatment or their relationship with the hospital and affiliated health care professionals.

If a participant chooses to discontinue with the intervention the principal investigator will phone the participant to understand reason for withdrawal.

Non-adherence to the trial will not be grounds for discontinuation as this is a feasibility trial, it is important to understand reasons for non-adherence.

Losses to follow-up

A participant will be considered lost to follow-up if he or she fails to partake in follow up surveys and is unable to be contacted by the principal investigator. The following actions must be taken if a participant fails to complete scheduled assessment:

- The principal investigator will attempt to contact the participant and reschedule the surveys and ascertain if the participant wishes to and/or should continue in the trial.
- Before a participant is deemed lost to follow-up, the investigator will make every effort to regain contact with the participant (where possible, 3 telephone calls and, if necessary, a certified letter to the participant's last known mailing address or local equivalent methods). These contact attempts will be documented in the participant's medical record.
- Should the participant continue to be unreachable, he or she will be considered to have withdrawn from the trial with a primary reason of lost to follow-up.

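### The study timeline puts baseline spirometry, CFQ-R and EQ-5D-Y after randomisation in an open-label trial; nothing requires them before families learn their arm, and the recruitment text conflicts on the questionnaires

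*Protocol*

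**What the plan says.** The Design paragraph reads: "This will be a pilot randomised, non-blinded, single center trial in children with CF attending the RCH on highly effective modulators". The Randomisation paragraph reads: "Randomisation will occur after consent in signed and will be performed by a person independent to the study". Its only safeguard on disclosure is that the chief investigator should not learn the allocation early. It does not say when families are told, and it does not make randomisation wait for any baseline measure.

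The study timeline in section 4 runs consent, randomisation, "Baseline data collection", then 3, 6 and 12 months. The Intervention and Control columns open at the randomisation row. Items C (demographics), D (spirometry) and E appear below it, once per arm. Item E is "CFQ-R & EQ-5D-Y (as part of the baseline questionnaire"), and item C is described as part of the same questionnaire.

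The prose differs in places. Under Recruitment, once consent is given, "Families will then complete the baseline demographic survey", and that survey asks permission to be contacted to "potentially participate in a qualitative interview via MS Teams if allocated to the intervention arm". Under Questionnaires, "A baseline demographic survey will be sent to all participants after online consent is gained", with no statement of its order relative to randomisation. The Spirometry paragraph gives no baseline window. Section 6 measures FEV1 change from study entry to study completion and does not define study entry.

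**The concern.** A baseline measured after participants know their arm is not guaranteed to be free of the allocation. CFQ-R and EQ-5D-Y are reported by the child or caregiver, and spirometry depends on effort, so in an open-label trial both could move with knowledge of the arm. As the timeline stands, entry spirometry could even be done after the intervention arm has received its onboarding material.

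The baseline matters in two planned analyses: the between-arm comparison of FEV1 change, and the quality-of-life area under the curve that feeds the cost per QALY. The Sample paragraph says the outcome data are meant to inform sample size for later full trials, so a distorted change score would carry forward. The order of procedures is protocol content, and an analysis plan cannot restore a pre-allocation baseline that was never taken.

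**Working it through.** There is no stated figure to reproduce. The minimum of 30 participants is set by precedent, without a power calculation. The check is a comparison of the text followed by algebra.

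**Order of events, by item**

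| Item | Study timeline | Other text | Result |
|---|---|---|---|
| C, demographics | After randomisation | Recruitment: straight after consent, with an item conditional on a future allocation | Conflict |
| E, CFQ-R and EQ-5D-Y | After randomisation | Not named in Recruitment, but shares the baseline questionnaire with C | Conflict by implication |
| D, spirometry | After randomisation | Spirometry paragraph: no baseline window. Section 6: study entry, undefined | Nothing offsets the timeline |

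**How a shift would pass into the analyses.** Let b be the shift in mean baseline in one arm relative to the other that is caused by knowing the arm, with 12-month values unaffected.

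- FEV1 change = FEV1 at 12 months − FEV1 at entry. The between-arm difference in change moves by −b, so the full size of the shift passes through with opposite sign.
- Quality of life: item E is scheduled only at baseline and 12 months. Assuming the trapezoidal rule, the area is (u0 + u12)/2 × 1 year, so the between-arm difference moves by b/2.
- The separate CFQ-R and EQ-5D-Y comparison in section 6 is of total scores and mentions no change from baseline. Baseline quality of life therefore enters mainly through the area under the curve.

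**Scale against sampling error.** Assume the minimum of 30 splits into 15 per arm, and take b = 0.2 SD purely as an illustration.

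- A difference in means has SE = sqrt(1/15 + 1/15) = sqrt(2/15) = 0.365 SD.
- FEV1 change, with b in SDs of the change score: 0.2/0.365 = 0.55 SE.
- Area under the curve, with b in SDs of a single score and rho the correlation between baseline and 12 months: the bias is 0.1 SD and the SE is 0.365 × sqrt((1 + rho)/2).
  - rho = 0: SE = 0.258, ratio 0.1/0.258 = 0.39.
  - rho = 1: SE = 0.365, ratio 0.1/0.365 = 0.27.

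On this illustration the shift is about half a standard error for FEV1 change and 0.27 to 0.39 of one for the area under the curve. All of these ratios scale in proportion to b, which the protocol does not give.

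**The case against.** The strongest reply is that the protocol nowhere says families know their arm when they answer the baseline questionnaire. A question about being interviewed if later allocated to the intervention makes sense only while the arm is unknown. Since demographics, CFQ-R and EQ-5D-Y share one questionnaire, the quality-of-life items may well be answered at the same point. This stands. A reader might infer from the timeline that baseline quality of life is certainly given with knowledge of the arm, but the documents support only a conflict between table and prose. The reply does not remove the problem, because Recruitment names only the demographic survey and no text places CFQ-R or EQ-5D-Y before randomisation. It does not reach spirometry at all.

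A second reply is that spirometry is done to international standards by experienced paediatric physiologists. This makes FEV1 less open to such influence than a questionnaire, but the test still depends on effort and no blinded assessment is described.

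A third reply is that little of importance is exposed. The primary objectives rest on survey and task completion, staff contacts, satisfaction and interviews, and none of these uses baseline FEV1 or quality of life. The trial is a pilot, and section 6 already expects wide intervals for costs. This also stands, and it limits the severity.

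Two further inferences are tempting but unsupported. One is that the baseline is spoiled as an adjustment covariate: section 6 plans t-tests, chi-squared tests or non-parametric alternatives and names no covariate adjustment. The other is that families will leave after allocation without any baseline. That is possible, but nothing in the protocol shows it. Some baseline data also come from the medical record, and repeated contact attempts are required before a participant counts as lost to follow-up.

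**Conclusion.** The point holds as a moderate one that should be fixed. The timeline puts baseline spirometry after randomisation in a non-blinded trial and no other text offsets this. For CFQ-R and EQ-5D-Y the timeline and the recruitment text disagree. Nothing withholds allocation from families until baseline is complete.

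Any shift would pass in full into the FEV1 change comparison and by half into the quality-of-life area under the curve. The second result assumes a two-point trapezoidal area over one year. The size of the shift is unknown, so the documents show an avoidable risk of bias in secondary and economic outcomes, not bias that has occurred. What argues for acting before recruitment is that a missing pre-allocation baseline cannot be recovered later, while the remedy is small.

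**What to change.** In the study timeline, move the baseline row (items C, D and E) above the randomisation row. In the Randomisation paragraph, state that allocation is released to families and the study team only after the baseline questionnaire is submitted and entry spirometry is recorded. In section 6, define study-entry FEV1 as that pre-allocation measurement. Align the Recruitment and Questionnaires text with the same order, naming CFQ-R and EQ-5D-Y as well as the demographic survey.

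If this order was always intended, the change is mainly to wording, plus a check in REDCap before allocation is released. The real cost is a delay between consent and allocation while spirometry is arranged. Its length cannot be estimated from the protocol: spirometry may be in person or by telehealth, clinics are quarterly, recruitment is planned for two months, and no turnaround time is given.
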